1.3 Rationale

1.3.1 Rationale for Conducting the Study

The androgen receptor (AR) is a member of the nuclear steroid hormone receptor family, which also includes ER and PgR. These are critical components of signaling pathways and regulate gene expression. AR expression in BC has long been noted and is the most common nuclear hormone receptor. AR is expressed in approximately 80% and 60% of primary and metastatic BC, respectively.³ Its expression varies across the different subtypes, approximately 84-95% in ER+ tumors, 50-63% in ER-/HER2+ cases and 10-53% in TNBC.³

The role of AR in BC still needs to be fully elucidated, differently from the well-known ER and PgR. Preclinical studies show that the androgen signaling pathway plays a critical role in the development of normal and malignant breast tissue. Epidemiologic studies suggest that increased levels of circulating androgens are associated with an increased risk for BC, primarily ER/PgR-positive BC.⁴

AR expression in ER+ BC associates with improved outcomes, but AR seems to be oncogenic in the tamoxifen-resistant setting.³ Approximately 30 to 50% of all ER+ BC tumors display *de novo* resistance to standard endocrine therapies and most metastatic ER+ tumors do eventually acquire resistance over time.⁵ AR positivity increases resistance to tamoxifen in BC models *in vitro* and *in vivo*.⁶ Thus, it is possible that acquired resistance to antiestrogen therapies could result from adaptation from estrogen dependence to androgen dependence.⁷

In the case of TNBC, signaling through the AR may play a role in pathogenesis. Studies which have focused on AR expression in TNBC have provided conflicting results in regards to the prognostic value of AR expression.⁸ While some studies suggest that AR expression is a favorable prognostic factor in patients with TNBC, others suggest that it predicts reduced survival in early TNBC.^{8, 9} Irrespective of this, AR might represent a new target in TNBC, which has so far a worse prognosis and very limited standard therapeutic options, none of them targeted.

As a result of these findings, AR has emerged as a potential useful marker for the further subclassification of BC and as a potential therapeutic target.

Modulation of AR signaling, either inhibitory or stimulatory, has previously been explored in BC with somewhat contrasting results. Androgen therapy has historically been used but largely abandoned in the 1970s due to its toxicity and the emergence of ER-directed therapies.

More recently, clinical reports of AR antagonism have been promising, especially in TNBC. Bicalutamide has been assessed in a phase II, single-arm trial in AR+, ER- advanced BC, and showed clinical benefit rate of 19% with a good safety profile.¹⁰ Some newer drugs like enzalutamide, have also been tested in TNBC. A phase II study in AR+ TNBC proved that this therapy was well-tolerated and showed promising clinical activity in selected patients.¹¹

These developments in combination with an improved understanding of AR signaling in different BC subtypes led to the renewed interest in targeting AR. However, the value of AR antagonists in the management of BC, the molecular alterations that occur after exposure to these agents and whether there are biomarkers useful to predict their effectiveness, still need to be fully elucidated. Increased understanding of AR blockade and its potential value in different BC subtypes and clinical testing of newer and more potent AR antagonists like darolutamide, is thus timely and necessary.

Translational Oncology Research Laboratories (TORL, at University of California Los Angeles, US) has conducted cell viability studies in 49 BC cell lines exposed to different concentrations of darolutamide. The studies have shown that cell lines belonging to each of the three BC subtypes (HR+, HER2+, TN) responded different to darolutamide. Responses are mainly seen in cell lines expressing AR but also in some lines that lack AR expression, suggesting that AR expression may not be the only biomarker predicting response to darolutamide (unpublished).

The current study will enroll EBC female patients with differing BC subtypes, with the intent of characterizing the molecular alterations in BC tissue before and after short-term exposure to the antiandrogen darolutamide. Studying the biological mechanisms in which darolutamide targets the AR in BC will be crucial in understanding its potential role in this disease, as well as providing the foundation for the rational development of darolutamide in the disease. Such information may suggest that darolutamide be combined with other modalities; for example, if treatment with the drug is discovered to affect multiple signaling pathways. Molecular profiling of tumor samples before and after darolutamide treatment may permit the identification of patients likely or unlikely to respond to the agent based on the biological and molecular characteristics of their tumors. Since it is essential to evaluate the molecular effects of darolutamide in tumors not previously exposed to chemotherapy or radiation, patients with untreated primary breast tumors amenable to a pre-

treatment biopsy followed by a post-darolutamide sample at definitive surgery or prior to starting neoadjuvant systemic therapy (NAST) represent an ideal population to study. Male patients will not be enrolled due to pathological and biological differences in male breast cancer.¹²

Although no direct benefit from the treatment with darolutamide is expected in the participating patients, the good tolerability and favourable safety profile of darolutamide at the selected dose, the proposed brief duration of treatment, and the fact that patients enrolled in the study will not be required to undergo any delay in definitive surgery or start of NAST if indicated, should ensure the safety and ethical set-up of the trial.

1.3.2 Rationale for Regimen and Dose Selection

In TRIO030, darolutamide will be given at a dose of 600 mg (2 × 300 mg tablets) b.i.d. to a daily dose of 1,200 mg. Darolutamide should be taken with food since exposure and C_{max} are reduced in fasting conditions.

Darolutamide has been studied in doses ranging from 100 mg to 900 mg b.i.d. in a phase I dose escalation and dose finding study. No dose-limiting toxicities were observed in this study and the maximum tolerated dose was not reached. Systemic exposure to darolutamide increased dose-proportionally in the dosing range from 100 to 700 mg b.i.d. At 900 mg b.i.d. dose there was no further increase in C_{max} or AUC observed when compared to 700 mg b.i.d. Based on the results of this phase I study, the recommended dose was 600 mg b.i.d. for further development. At the dose of 600 mg b.i.d. most AEs were grade 1-2 and assessed by the Investigators as not related to protocol treatment.

Therefore, the dose selected in the study is considered as safe and is the dose that is being used in current darolutamide trials in patients with other primary cancer sites.

2. OBJECTIVES

2.1 Primary Objective

- To identify the molecular alterations that occur in human BC tissue, following short-term exposure to darolutamide in female patients with EBC.

2.2 Secondary Objectives

- To evaluate the safety and tolerability of short-term exposure to darolutamide in female patients with EBC.

3. STUDY DESIGN

3.1 Overall Study Design and Plan: Description

This is a multi-center, open-label, tissue-acquisition study involving up to 60 patients with early-stage invasive BC.

Female patients with (a) suspicion of invasive BC based on clinical and/or radiological findings, or (b) those who have a confirmation of invasive BC based on previous cytology/core/incisional biopsy will be invited to participate in the study:

- (a) In cases without pathological confirmation of BC diagnosis, signature of patient informed consent form (PICF) before BC confirmation biopsy is preferred to allow the collection of study-specific biopsies to be conducted.

(b) For patients who have already had a confirmatory biopsy, they may also participate in the study if willing to undergo a subsequent study-specific biopsy procedure according to the protocol or if their diagnostic biopsy has been done according to the protocol requirements (in terms of number of cores/tissue, fresh frozen collection, etc.; refer to section 6.5.7.1).

At time of PICF signature, patients will be registered in the study. Primary tumor samples will be collected by core needle biopsy or incisional biopsy (excisional biopsy will not be allowed). A minimum of three cores of tissue using a 14-gauge needle is recommended (or equivalent amount with an incisional biopsy). Two of the cores will be snap-frozen and the third one should be prepared in paraffin according to site's practice. In cases that it is not possible to provide enough material, collection of 2 cores (or equivalent amount with incisional biopsy) will be acceptable; one core will be snap-frozen and the other one will be prepared in paraffin.

After all screening procedures and confirmation of eligibility, patients will be enrolled and will begin intake of darolutamide. To be able to assess the molecular alterations after darolutamide exposure in different BC subtypes, female patients being either triple-negative, or HR+/HER2 negative, or HER2 positive will be enrolled in the study. Up to 20 patients with each of these subtypes will be included (refer to section 6.1.2.2 for further details on the enrollment according to BC subtype). However, a minimum of 8 evaluable patients in each cohort is considered acceptable if enrollment of 20 patients is not feasible within a cohort for any reason.

Eligible patients will be enrolled and receive darolutamide at a dose of 600 mg (2 × 300 mg tablets) b.i.d. corresponding to a daily dose of 1,200 mg. Protocol treatment should start within 5 days of enrollment and within 42 days of the study-specific tumor sample collection. Patients enrolled, but not treated, will be discontinued from study and managed as per the site's standard of care (SoC). Minimum duration of treatment with darolutamide is 14 days with a recommended maximum duration up to 21 days. It is recommended that the BC surgery/pre-NAST biopsy date is defined prior to starting protocol treatment. The start date of darolutamide (Day 1) will be derived as minus 14 to 21 days from the scheduled BC surgery/pre-NAST biopsy date. Treatment will be taken until the day prior to the BC surgery (if NAST is not indicated) or the day before NAST starts if indicated; or when the patient is ordered to stop all oral intake, whichever occurs first (refer to section 5.3.2.1). If for some reason surgery takes place more than 21 days after treatment start (e.g. surgery scheduling issues, surgery delays, etc.) it is acceptable that patient receives darolutamide for more than 21 days and up to a maximum of 35 days. Patient should continue protocol treatment until the day prior to BC surgery/pre-NAST biopsy or "*nil per os*" (npo) is ordered. In these cases it is strongly recommended to have BC surgery/pre-NAST biopsy performed as soon as possible after 21 days of treatment are completed.

At the time of BC surgery (if NAST is not indicated), or before NAST starts if indicated, BC tissue will be collected: two cores (or an equivalent amount of tissue), one fresh-frozen and one paraffin-embedded.

End of Study (EoS) visit will occur 30 days (+/- 3 days) after the patient's last intake of darolutamide. In case protocol treatment-related AEs/SAEs ongoing at the time of the EoS visit, monitoring of these events will continue as clinically indicated until (a) the events have resolved or (b) the events have reached a status which, in the Investigator's opinion, is unlikely to resolve due to the nature of the condition and/or the patient's underlying disease.

Treatment for BC including NAST (if applicable), definitive surgery, and adjuvant therapy will be at the Investigator's discretion.

[figure not shown]

Figure 1: Study Schema

BC= Breast cancer

* In cases with absence of a pathological confirmation of BC diagnosis, PICF signature prior to the biopsy for BC confirmation is preferred. For patients who already had such confirmatory biopsy, they may also participate in the study if willing to undergo a subsequent study-specific biopsy procedure according to the protocol or if their diagnostic biopsy has been done according to the protocol requirements (in terms of number of cores/tissue, fresh frozen collection, etc.).

3.2 Number of Patients and Investigational Sites

Up to 60 patients will be enrolled in the study, from approximately 20 sites in North America and Europe, with an acceptable minimum of 8 evaluable patients in each if enrollment of 20 patients is not feasible within a cohort for any reason. The list of Investigators participating in the study will be maintained in TRIO's Clinical Trial Management System.

3.3 Study End

The study will end once the last patient undergoes the EoS visit and all data required for the analyses have been observed, collected and cleaned. The trial may be prematurely terminated at any time by Ethics Committees (EC)/Institutional Review Boards (IRB), competent authorities, or the sponsor. Potential reasons for premature termination of the study by the sponsor are (not exhaustive):

- Regulatory authority decision
- Change in opinion of the EC/IRB
- Drug safety concerns
- Manufacturer's decision to discontinue development of darolutamide
- Inability to run the study because of operational issues (e.g., low recruitment)

If the study is prematurely terminated or discontinued, TRIO will promptly notify the Investigators and all other relevant parties.

4. PATIENT SELECTION

Patients can be enrolled in the study only if the eligibility criteria are met. This study can fulfill its objectives only if appropriate patients are enrolled. Patients who fail to meet all inclusion criteria or fulfill at least one exclusion criteria cannot be enrolled in the study. The sponsor will not grant any eligibility waivers.

If a patient whom does not meet the eligibility criteria is incorrectly enrolled, the Investigator should immediately inform the Medical Monitor. The decision about the continuation or discontinuation of this patient on protocol treatment will be based on medical judgment, treatment benefit and safety risks for her.

4.1 Inclusion Criteria

1. Signed and dated PICF obtained prior to initiation of any study-specific procedure and treatment.
2. Female \geq 18 years old.
3. Histologically proven invasive breast carcinoma (through either a core needle biopsy or an incisional biopsy) for which surgery is indicated as the primary treatment modality. Patients for which NAST is indicated are also eligible provided they are willing to undergo a biopsy (as per requirements in section 6.5.7) after completing treatment with darolutamide and prior to NAST start.
4. Known ER, PgR and HER2 statuses.
5. Tumor must be confined to either the breast or to the breast and ipsilateral axilla (*Note: patients with multifocal/multicentric tumors are eligible*). Patient must have (according to TNM 7th edition rules):
 - T1 with T \geq 1.0 cm, T2 or T3 by at least one radiographic or clinical measurement
 - Either clinically positive (N1 only) or clinically negative axillary nodes (N0)
 - M0
6. Eastern Cooperative Oncology Group (ECOG) performance status (PS) of 0 or 1.
7. Adequate organ function within 28 days prior to enrollment, as defined by the following criteria:
 - Hematology:
 - Hemoglobin \geq 9.0 g/dL,
 - ANC \geq 1.5 \times 10⁹/L,
 - Platelet count \geq 100 \times 10⁹/L
 - Liver function:
 - ALT and AST \leq 2.5 \times ULN,
 - Total bilirubin \leq 1.5 \times ULN (or \leq 3 times ULN for patients with documented Gilbert's syndrome or for whom indirect bilirubin concentrations suggest an extra-hepatic source of elevation)
 - Renal function: Creatinine \leq 2.0 \times ULN
8. No more than 42 days should elapse from the day study-specific tumor sample is taken at initial diagnosis (or subsequent procedure) to the day of the first intake of darolutamide.
9. WoCBP* must agree to use acceptable non-hormonal contraceptive methods of birth control from the day of the screening pregnancy test and up to 3 months after the last intake of darolutamide.
10. For WoCBP* negative serum pregnancy test within 7 days of enrollment.
11. Willingness and ability to comply with scheduled visits, treatment plans, laboratory tests, and biopsies as detailed in the protocol.

** Note: Women of childbearing potential (WoCBP) are any women between menarche and menopause who have not been permanently sterilized, capable of procreation. Permanent sterilization includes hysterectomy and/or bilateral oophorectomy and/or bilateral salpingectomy but excludes bilateral tubal ligation/occlusion. Postmenopause is defined as:*

- *Bilateral oophorectomy*
- *Age \geq 60*
- *Age < 60 and amenorrheic for ≥ 12 months in the absence of an alternative medical cause and FSH and estradiol in postmenopausal ranges.*

4.2 Exclusion Criteria

1. Any T0, Tis, T1 < 1.0 cm, T4; or N2-3; or M1 BC.
2. Bilateral invasive BC.
3. Patient that underwent excisional biopsy of the primary tumor.
4. Medical indication or patient desire to undergo BC surgery or start NAST prior to completing at least 14 days of treatment with darolutamide, and/or refusal of patient to undergo corresponding biopsy in case NAST is planned.
5. Prior or concurrent systemic anticancer therapy for BC treatment (immunotherapy, biologic/targeted therapy, chemotherapy, investigational agents).
6. Prior or concurrent ipsilateral radiation therapy for invasive or noninvasive BC.
7. Prior or concurrent treatment or preventative use of any hormonal agent such as aromatase inhibitors (AI), fulvestrant, raloxifene, tamoxifen or other SERM, or with any other hormonal agent used for the treatment or prevention of BC or for any other indication (e.g. osteoporosis).
8. Concurrent use of ovarian hormone replacement therapy. Prior treatment should be stopped at least 28 days prior to registration.
9. Prior or concurrent treatment with AR antagonists or CYP17 enzyme inhibitor.
10. Use of other investigational drug within 28 days of enrollment.
11. Major surgery* within 28 days before enrollment.
12. Any concurrent or previous malignancy within 5 years prior to enrollment except for basal or squamous skin cancer, or carcinoma in situ of the cervix, or other non-invasive/in-situ neoplasm, all of which must have been adequately and radically treated. A patient with previous history of invasive malignancy (other than adequately and radically treated basal or squamous skin cancer) is eligible provided that she has been disease free for more than 5 years.
13. Severe or uncontrolled concurrent disease, infection or comorbidity.
14. Known active viral hepatitis, HIV or chronic liver disease.
15. Other serious illness or medical condition within 6 months before enrollment, including any of the following: Concurrent congestive heart failure NYHA Class III or IV, severe/unstable angina pectoris, myocardial infarction, uncontrolled hypertension, coronary/peripheral artery bypass graft, high-risk uncontrolled arrhythmias, stroke.
16. Any contraindication to oral agents or gastrointestinal disorder or procedure which expects to interfere significantly with absorption of protocol treatment.
17. History or current evidence of any condition, therapy, or laboratory abnormality that might confound the results of the trial, interfere with the patient's participation for the full duration

of the trial, or is not in the best interest of the patient to participate, in the opinion of the treating Investigator.

18. Known psychiatric or substance abuse disorders that would interfere with cooperation with the requirements of the trial.
19. Known allergy to darolutamide or any of the excipients.
20. Pregnant or lactating patients.

* Note: Major surgery defined as requiring a general anesthesia or respiratory assistance; involving openings into the great cavities of the body, organs removed, or normal anatomy altered; implying risks of severe hemorrhage; implying risk for life of the patient or severe disability.

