5.3.2 Standard Treatment Schedule

5.3.2.1 Dosage and Administration

Darolutamide will be given at a dose of 600 mg (2 × 300 mg tablets) b.i.d. to a daily dose of 1,200 mg.

The following timelines will be considered for darolutamide administration (refer to Figure 1: Study Schema):

- Darolutamide shall be administered starting within 5 days of enrollment.
- No more than 42 days should elapse from the day the study-specific tumor sample is taken at initial diagnosis (or in a subsequent procedure) to the day of the first intake of darolutamide (*Note: for patients who already had their initial diagnostic biopsy prior to registration and this procedure has been done according to the protocol requirements, the 42- day window should be counted from the date of such biopsy*).
- Minimum duration of treatment will be 14 days prior to BC surgery or to the pre-NAST biopsy (if NAST is indicated) (*Note: a day of treatment is considered as any day where the patient takes any darolutamide intake*)
- A maximum duration of 21 days of treatment is recommended. It is recommended that the date of BC surgery/pre-NAST biopsy is defined prior to starting protocol treatment. The start date of darolutamide (Day 1) will be derived as minus 14 to 21 days from the scheduled BC surgery/pre-NAST biopsy date.
- Treatment will be given until the day prior to the BC surgery, or the day before pre-NAST biopsy or when npo is ordered, whichever occurs first.
- If for some reason BC surgery/pre-NAST biopsy takes place more than 21 days after treatment start, it is acceptable that patient receives darolutamide for more than 21 days and up to a maximum of 35 days; patient should continue protocol treatment until the day prior to BC surgery/pre-NAST biopsy or npo is ordered. In these cases it is strongly recommended to have BC surgery/pre-NAST biopsy done as soon as possible after 21 days of treatment are completed. Also, in any case that treatment is extended beyond 21 days, TRIO Medical Monitor should be contacted to discuss continuation of treatment and the need for assessments.

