5.5 Concomitant Medications and Procedures

Concomitant medications and procedures to be documented in patients' medical sources and collected in eCRF include any medication or therapeutic procedure (e.g. prescription drugs, over-the-counter drugs, herbal/homeopathic remedies, nutritional supplements, blood transfusions, etc.) used by a patient from 7 days prior to enrollment until the EoS visit.

Patients will be instructed to consult with the Investigator before taking any medications (including over-the-counter medications).

Supportive medications may be provided prophylactically or therapeutically per Investigator discretion.

Any concomitant treatment not listed in the section 5.5.2 is considered permitted in the study and may be prescribed as clinically appropriate during the study.

Concomitant therapies will be assessed at all visits and must be recorded on the appropriate eCRF according to the rules in section 6.5.4.

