6.1.2 Registration and Enrollment

6.1.2.1 Registration and Enrollment Procedures

At time of PICF signature patients will be registered in the study and then will undergo screening procedures. After all screening procedures and confirmation of eligibility, patients will be enrolled.

The following steps for registering and enrolling a patient are chronologically performed:

1. The patient must provide written informed consent prior to performing any study-specific procedure not considered standard practice by the institution.
2. The site will ask TRIO for patient's registration immediately after signature of PICF. A unique registration number will be assigned to each patient in the study.
3. The site will proceed to perform the protocol-required biopsy and all screening procedures according to section 6.3. Upon completion of screening procedures, the Investigator or his/her delegate will check if the patient meets all eligibility criteria:
 - Patients who do not meet all eligibility criteria: sites will have the screen failure form completed in Remote Data Capture (RDC) with corresponding screen failure reason captured.
 - Patients who meet all eligibility criteria: sites will enter the screening data in RDC which will be reviewed centrally by TRIO. After the review of the eligibility criteria, TRIO may address, if necessary, some discrepancies that will have to be answered by the site. Once the eligibility central review is completed and discrepancies have been resolved (if applicable) TRIO will provide the confirmation that the patient is eligible and the site will be able to move forward with the patient's enrollment in RDC. The site will receive a confirmation of enrollment. If the patient is deemed not eligible following the central eligibility review, the site will be asked to report the screen failure reason in RDC.

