6.5.7.1 Breast Tumor Tissue Collection

Collection of the following samples is mandatory in the study:

- **Pre-treatment:** A breast tumor sample must be collected at the time of the initial diagnosis (or in a subsequent procedure) either by core needle or incisional biopsy. Excisional biopsy will not be allowed.

A minimum of 3 core biopsies using a 14-gauge needle (or the equivalent with an incisional biopsy) is recommended to perform the protocol-defined molecular analyses. Once the core biopsies have been removed, two of the cores (or equivalent amount of tumor) must be immediately snap-frozen using the procedure outlined in the study laboratory manual, then stored in liquid nitrogen or at -70 to -80 degrees Celsius at the site. The third sample should be prepared in paraffin according to site's practice. In cases it is not possible to provide enough material, collection of 2 cores (or equivalent amount with incisional biopsy) will be acceptable: one core will be snap-frozen and the other one will be prepared in paraffin.

In patients with multifocal or multicentric tumors, efforts will be made to obtain samples from each discrete lesion.

For patients who already had the confirmatory biopsy prior to registration, there is no need to repeat it provided that their diagnostic biopsy has been done according to the protocol requirements (in terms of number of cores/tissue, fresh frozen collection, etc.).

- **BC surgery/Pre-NAST biopsy:** An amount of BC tissue equivalent to two cores (or 2 cores of tissue) must be collected at the time of the patient's surgery (if no NAST indicated) or at time of the pre-NAST biopsy (if NAST is indicated). The pre-NAST biopsy should be done before NAST start. Half of the tissue will be prepared as fresh-frozen, the other half in paraffin.

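### The 28-day hormone-replacement washout runs to registration, not to the baseline tissue, so an accepted pre-registration biopsy may have had a short washout or none

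*Protocol*

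**What the plan says.** Protocol section 4.2, exclusion 8, bars "Concurrent use of ovarian hormone replacement therapy" and then sets the condition for past users: "Prior treatment should be stopped at least 28 days prior to registration". Registration is tied to consent (section 6.1.2.1): "At time of PICF signature patients will be registered in the study and then will undergo screening procedures".

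Baseline tissue need not follow registration. Section 6.5.7.1 states: "For patients who already had the confirmatory biopsy prior to registration, there is no need to repeat it", provided that the earlier biopsy met the protocol's tissue requirements, which include frozen material. The time limit on baseline tissue is inclusion 8 in section 4.1: "No more than 42 days should elapse from the day study-specific tumor sample is taken at initial diagnosis" to first intake (a later study biopsy is counted the same way). For a pre-registration biopsy, section 5.3.2.1 says that "the 42- day window should be counted from the date of such biopsy". Footnote 1 to Table 2 exempts both consent and the screening tissue from the 28-day screening window.

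Medication is recorded if it was "used by a patient from 7 days prior to enrollment until the EoS visit" (section 5.5; section 6.5.4 gives the same look-back). The primary endpoint (section 6.5.7.2) compares tissue before and after darolutamide, with AR, ER, PgR, HER2, ki67 and cytokeratins 5 and 6 as the minimum marker set. Section 8.6 makes that comparison descriptive.

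**The concern.** The washout protects an administrative date rather than the sample on which the primary comparison rests. If the biopsy comes first and registration several weeks later, a woman can satisfy the 28-day condition although her baseline tissue was taken soon after stopping hormone replacement, or while still on it. Her post-treatment tissue is then taken well after the stop.

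The study has no control arm, so the before-after change is the only evidence on darolutamide. In such a patient two things change between the samples, hormone replacement and darolutamide, and the comparison cannot separate them. ER, PgR, AR and ki67 are the listed markers for which this matters most.

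The data rules would not reveal the problem. Hormone replacement stopped at least 28 days before registration was also stopped at least 28 days before enrolment, which is at least 28 - 7 = 21 days outside the medication look-back. The history collected under section 6.5.1 covers diseases, symptoms and hypersensitivity, and does not mention drug stop dates.

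**Working it through.** The plan gives no figure to reproduce. The check is a count of days.

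**Inputs**
- Washout: at least 28 days before registration (4.2, exclusion 8).
- Biopsy to first intake: at most 42 days (4.1, inclusion 8; 5.3.2.1).
- Treatment before the post-treatment sample: 14 to 35 days (Table 2, footnote 2).
- Registration to first intake, L days: not given. Taken here as 0 to 15 as an assumption.

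**Set-up.** Let day 0 be the accepted pre-registration biopsy, s the day hormone replacement stops (negative if before the biopsy), r the day of registration and d the day of first intake. The rules require r ≥ s + 28, d = r + L and d ≤ 42.

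**Guaranteed washout at biopsy.** From s ≤ r - 28, the biopsy is at least 28 - r days after the stop, where r is also the biopsy-to-registration gap:
- gap 7 days: 28 - 7 = 21 days
- gap 14 days: 28 - 14 = 14 days
- gap 21 days: 28 - 21 = 7 days
- gap 28 days: 28 - 28 = 0 days
- gap 35 days: 28 - 35 = -7, so use may continue for 7 days after the biopsy

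**When the baseline can be on hormones.** This needs s ≥ 0 (stopping on the biopsy day counts as zero washout), hence r ≥ 28. The 42-day limit gives r ≤ 42 - L. The latest permitted stop is day 42 - L - 28 = 14 - L.

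| L (days) | Gaps allowing an on-hormone baseline | Latest stop after biopsy |
|---|---|---|
| 0 | 28 to 42 days | day 14 |
| 5 | 28 to 37 | day 9 |
| 7 | 28 to 35 | day 7 |
| 10 | 28 to 32 | day 4 |
| 14 | exactly 28 | day 0 |
| 15 | none | none |

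**Post-treatment sample in those cases.** The shortest time off hormones is 28 + 14 = 42 days (L = 0). The longest is 42 + 35 = 77 days (stop on day 0, first intake on day 42).

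**Worked example.** Biopsy on hormones on day 0, stop on day 10, registration on day 38 (28 days later), first intake on day 42. The post-treatment sample falls between day 42 + 14 = 56 and day 42 + 35 = 77, which is 46 to 67 days off hormones.

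**German version 5.0 (synopsis in SAP appendix 5.2).** First intake must come within 7 days of the pathology report, so the gap is at most the report lag plus 7 days. An on-hormone baseline needs a report lag of at least 28 - 7 = 21 days. A 7-day lag leaves a guaranteed washout of 28 - 14 = 14 days.

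**The case against.** The strongest reply is that the path is narrow. Consent before the diagnostic biopsy is preferred (section 3.1), and where the study biopsy follows registration the washout already precedes the tissue. Only a pre-registration biopsy that happened to include frozen tissue is exposed. The calendar is also tight. If hormones stop on the biopsy day, 42 - 28 = 14 days remain for screening, central eligibility review, enrolment and first intake. If they stop only when pathology reports, the report lag comes off those 14 days: an assumed 7-day lag leaves 7 and a 14-day lag leaves none. All of this stands, and it limits the point to a minor one.

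A second reply is that other exclusions catch these patients. A reader might infer from the day count that such a woman meets every eligibility rule. The documents do not support that. Exclusion 17 lets the investigator exclude for a therapy that could confound the results, and exclusion 7 has broad wording on prior hormonal agents for any indication. Neither closes the gap, however. Exclusion 17 is a matter of opinion, and exclusion 8 expressly admits past hormone replacement, which leaves the reach of exclusion 7 unclear. Neither sets a date rule tied to the tissue.

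A third reply is that molecular analysis details sit in separate documents (protocol 6.5.7; SAP 3.1.3). That also stands: it cannot be said that those documents lack such a check, only that the protocol and SAP do not contain one.

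**Conclusion.** The point holds as a minor gap. For patients whose pre-registration biopsy is accepted as baseline, exclusion 8 guarantees only 28 days minus the biopsy-to-registration gap, and nothing at gaps of 28 to 42 - L days. This rests on L, which the documents do not give; from L = 15 days an on-hormone baseline is impossible and only a shortened washout remains. German version 5.0 nearly closes the path.

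Three stronger readings should be avoided:
- A reader might infer that some baseline samples were in fact taken on hormones. The documents give neither the number of past users nor the number of accepted pre-registration biopsies, so the count may be zero.
- A reader might infer that a false darolutamide effect would result. The documents give no size or direction for the effect of hormone withdrawal on these markers. What follows is only that the two influences could not be separated in such a patient.
- A reader might take 28 days as the longest compliant washout at biopsy. It is a minimum to registration, so there is no upper limit.

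For scale only, one patient would be 1/19 = 5.3% of the HR+/HER2 negative patients enrolled (SAP 2.3). That is enrolled rather than evaluable patients, and it is not an estimate of impact.

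**What to change.** No eligibility rule needs to change, and enrolment closed on 14 February 2019. In the molecular analysis:

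1. For every past user of hormone replacement, retrieve the stop date from source. Sites needed it to apply exclusion 8, so it should be available.
2. Flag patients whose baseline sample was taken before that date or less than 28 days after it, which is the protocol's own interval.
3. Repeat the change summaries for ER, PgR, AR and ki67 without the flagged patients, next to the main summaries. If nobody is flagged, say so in the report; that rules the problem out.

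The cost is one extra data item for past users and one sensitivity summary on slightly fewer patients.
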